4.1 Inclusion Criteria

To be eligible for study participation, a volunteer must satisfy all of the following inclusion criteria:

1. Age ≥ 18 years.
2. Documentation of HIV-1 infection by any licensed ELISA test and confirmed by a Western Blot.
3. Receiving a DHHS-approved ARV regimen,.
4. Level of cell-associated HIV RNA ≥ 5 copies/million peripheral blood mononuclear cells (PBMC) done at screening visit 1
5. HIV-1 RNA levels less than detectable by current commercial means (e.g., Roche Amplicor, b-DNA test) for a minimum of 12 months prior to screening at all time points, and with at least 2 measurements in this 12 month window.

6. CD4 ≥ 300 cells/mm³ at pre-entry visit within 14 days prior to enrollment.
7. Ability to sign informed consent and willingness to comply with the study requirements and clinic policies.
8. No evidence of viral hepatitis co-infection as assessed by Hepatitis C antibody, HCV RNA, and hepatitis B surface antigen; determinations at pre-entry visit within 28 days prior to enrollment.
9. No history of or evidence of autoimmune hepatitis or other autoimmune disorders at screening, or antinuclear antibody (ANA $> 3x$ upper limit of normal).
10. Laboratory values at pre-entry visit within 14 days prior to enrollment:
 - Alkaline phosphatase < 2.0 times upper limit of normal
 - Alanine transaminase (ALT) < 2.0 times upper limit of normal
 - Total bilirubin < 2.5 mg/dL (< 40 mg/dL if on Atazanavir)
 - Creatinine clearance ≥ 60 mL/min as estimated by the Cockcroft-Gault equation
 - Neutrophil count ≥ 1500 cells/mm³
 - Platelets $\geq 150,000$ / mm³
 - Hemoglobin ≥ 12.0 mg/dL for men and > 11.0 g/dL for women
 - Fasting glucose < 126 mg/dL
11. No history or evidence of significant clinical depression at screening that in the opinion of the investigator would affect the ability of the patient to participate in the study, or which would constitute a threat for his/her health in case of relapse upon INF treatment. The Beck Depression Inventory score must be ≤ 13 at pre-entry visit.
12. No history of INF/PEG-INF therapy.
13. If capable of pregnancy: use of effective contraception during study: effective contraception methods include abstinence, surgical sterilization of either partner, barrier methods such as diaphragm, condom, cap or sponge, or use of hormonal contraception with an anti-HIV regimen that will not alter metabolism of hormonal contraception.
14. Participants must have primary medical care outside this protocol: participants will have to provide Primary Care Doctor's contact information.

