5.3 Pre-Entry Visit 2: Leukapheresis Visits (Day -14 to Day -1, Day 28)

Once the subject has been found to meet the eligibility criteria, the subject will return for leukapheresis for the purposes of peripheral blood lymphocyte (PBL) storage for use in future virologic and immunologic studies. Leukapheresis, will be scheduled to occur at Pre-Entry 2 and during Visit 4 (Day 28).

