8.2 Toxicity Management

Specific expected toxicities lower than grade 4 will be managed as follows:

Adverse Event Action

Neutropenia	Participants who experience Grade 3 neutropenia will receive filgrastim at 300 µg subcutaneously up to 3 times a week. Absolute neutrophil counts will be monitored until return to subject's baseline or <Grade 1. Patient will be asked to return in 1-3 days for evaluation. If grade 3 neutropenia has resolved, patient will return 2-3 days later for repeat evaluation. If grade 3 neutropenia has not resolved at the day 1-3 visit, additional G-CSF will be administered
-------------	--

and the patient will return daily for evaluation and additional G-CSF as medically indicated until resolved. Filgrastim will be discontinued at this time. Interferon will be continued for Grade 3 neutropenia.

CD4 cell count	If the CD4 count declines to <14%, pneumocystis prophylaxis will be offered until the percentage of CD4 cells increases to ≥14%.
Depression	If a BDS score of 14-19 is reported, assessment by the site investigator will be scheduled before the next dose of study drug. If a BDS score of 20-28 is reported, a psychiatric evaluation is required before the next dose of study drug. If a BDS score is >29 or suicidal ideation is reported, participants will permanently discontinue study drug and undergo prompt psychiatric evaluation.

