12.1.4 Potential for Adverse Effects from Leukapheresis

Risks associated with leukapheresis are similar to those seen with whole blood transfusions. They rarely include infection (<1% of persons) and commonly include nausea, fainting, dizziness, bruising at the needle puncture site, blood loss, and a transient decrease in platelet or red blood cell counts in 10% to 25% of persons. Potential problems of a leukapheresis procedure when citrate is given intravenously as an anticoagulant rarely includes seizures in <1% of persons and commonly includes muscle cramping, numbness, chilling, tingling sensations, and feelings of anxiety. Citrate is approved by the Food and Drug Administration for this use. If citrate/heparin or heparin alone is used as the anticoagulant, there may be a transient increase in clotting time, which may lead to blood loss in very rare instances (<1%). There is also a small risk of technical problems with the apheresis machine (1:1000 phereses).

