12.1.5 Risks of Phlebotomy

The primary risks of phlebotomy include occasional bleeding or bruising of the skin at the site of needle puncture, and the sensation of transient lightheadedness or rarely, fainting or infection. The amount of blood drawn for research purposes shall not exceed 10.5 mL/kg or 550 mL, whichever is smaller, over any 8-week period.

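### The men's hemoglobin entry limit is printed in mg/dL and the women's in g/dL; the men's unit should be g/dL

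*Combined protocol and SAP*

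**What the plan says.** Section 4.1 introduces its list by stating that "a volunteer must satisfy all of the following inclusion criteria". Item 10 lists the laboratory values, which are taken at the pre-entry visit within 14 days before enrollment. The hemoglobin line reads "Hemoglobin ≥ 12.0 mg/dL for men and > 11.0 g/dL for women".

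Section 5.3 then makes eligibility the condition for the first apheresis: "Once the subject has been found to meet the eligibility criteria, the subject will return for leukapheresis". That visit falls between Day -14 and Day -1.

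**The concern.** One analyte in one line carries two units a thousandfold apart. Read as written, the criterion sets a real floor for women and none for men.

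This is an operative threshold, not background text. The complete blood count at Pre-entry Visit 1 (section 5.2) is the listed hemoglobin check before the first leukapheresis, and item 10 is the standard by which that result is judged. The next scheduled counts come later, at Day 0 (section 5.4) and before each dose (sections 5.5 and 7.3).

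The protocol gives its own reasons for wanting a hemoglobin floor here. Among the common effects of leukapheresis, section 12.1.4 lists "a transient decrease in platelet or red blood cell counts in 10% to 25% of persons". Section 12.1.5 says research blood draws "shall not exceed 10.5 mL/kg or 550 mL, whichever is smaller, over any 8-week period". As printed, a man with low hemoglobin could be enrolled without breaching the written limit, so a monitor could not cite that line against the enrollment.

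**Working it through.** **Inputs, both from section 4.1, item 10**

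- Men: "Hemoglobin ≥ 12.0 mg/dL for men"
- Women: "> 11.0 g/dL for women"
- Conversion: 1 g/dL = 1000 mg/dL

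The plan derives no figure here that could be reproduced. The check is a unit conversion, followed by a search for any other limit that might govern.

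**Step 1: the men's limit as printed.** 12.0 mg/dL / 1000 = 0.012 g/dL.

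**Step 2: its size against the alternatives.**

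- Against the same number in g/dL: 12.0 / 0.012 = 1000.
- Against the women's limit: 11.0 / 0.012 = 917 (rounded).

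**Step 3: which unit is wrong.** There are two ways to make the line consistent.

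| Unit for both sexes | Men | Women | Result |
|---|---|---|---|
| mg/dL | 12.0 / 1000 = 0.012 g/dL | 11.0 / 1000 = 0.011 g/dL | Neither limit excludes anyone |
| g/dL | 12.0 g/dL | 11.0 g/dL | Men's limit 1.0 g/dL above women's; both can exclude |

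Only g/dL gives a criterion that does anything, so the error is in the men's half.

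**Step 4: whether another section supplies the limit.**

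- Section 4.2 (exclusions) names autoimmune hemolytic anemia but gives no hemoglobin value.
- Sections 5.2 to 5.10 and Appendix 1 call only for a complete blood count.
- Section 7.3 requires the count to be reviewed before each dose but sets no hemoglobin value.
- Section 8.2, introduced by "Specific expected toxicities lower than grade 4 will be managed as follows", covers neutropenia, CD4 count and depression.
- Section 8.3 (permanent discontinuation) does not name hemoglobin.
- Appendix 2 refers to an external scale for grading adverse events. It is not cited as a source of entry limits.

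None of these corrects the line or supports mg/dL.

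**The case against.** The strongest objection is that the line corrects itself. The women's half shows the unit, the numbers 12.0 and 11.0 make sense only in g/dL, and no clinician would take 0.012 g/dL as a real floor. For harm to follow, staff would have to apply the misprint literally after seeing the pre-entry count, and the investigator would have to leave the discretionary exclusion (section 4.2, item 17) unused. Counts and safety tests are also reviewed before dosing (sections 7.3 and 9.1). On this view the point is copy-editing, and the factors of 1000 and 917 only measure the misprint.

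Most of that stands. The likely effect on enrollment is near zero, and the ratios should not be read as an effect size. The reviews before dosing come after the first leukapheresis, so they do not protect that step, but the pre-entry count and investigator judgment do.

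The leukapheresis percentage also needs care. It closes a list of common effects and may apply to the whole list. Even on the narrower reading it covers platelets or red cells, so it is not a rate of red-cell decline.

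A text-conversion error cannot be ruled out entirely. It would have had to add a letter to one unit and leave the other intact in the same line, and a look at the source page settles it.

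None of this makes the printed limit correct. An entry criterion should not depend on readers repairing it.

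**Conclusion.** The concern holds. The men's hemoglobin limit in section 4.1, item 10 is printed a thousandfold too low and, taken literally, excludes no man. The intended value is 12.0 g/dL.

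The point is minor. It is a drafting slip in a safety-related entry threshold, with no bearing on the endpoint, the sample size or any analysis. The view that the practical effect is close to zero assumes that sites read the unit as g/dL, which is very likely but which the document does not state.

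**What to change.** In section 4.1, item 10, change the men's unit from mg/dL to g/dL, so that the limits read at least 12.0 g/dL for men and above 11.0 g/dL for women. If the sites use an eligibility checklist or screening form that repeats the line, correct it there too; the protocol does not mention one. The cost is one unit in the next amendment.

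While that list is open, the authors could also confirm the bilirubin limit for participants on atazanavir. It appears as 40 mg/dL, which is 40 / 2.5 = 16 times the ordinary limit, and a decimal point may have been lost when the text was converted. That is a query only, and nothing above depends on it.

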4.2 Exclusion Criteria

A volunteer will be ineligible to participate in this study if any of the following criteria are met:

1. History of neoplastic disease requiring cytotoxic therapy including hydroxyurea.
2. Use of long-term systemic corticosteroids, immunosuppressive agents, or cytotoxic agents within 60 days prior to enrollment.
3. Any vaccination within 30 days prior to enrollment. Individuals interested in participating who require vaccination will delay screening until 30-day period is completed.
4. Concurrent therapy with investigational cytokines including IL-2 or IL-12 during the course of the study. Prior administration of cytokines is not an exclusion criterion; at least 4 months from most recent cycle of IL-2 or IL-12 is required.
5. Any febrile illness (>38°C) in the 3 weeks prior to enrollment or any acute therapy for a serious infection completed within 30 days prior to enrollment.
6. Current pregnancy or lactation, history of pregnancy in the last 4 months.
7. Preexisting autoimmune disorders including inflammatory bowel diseases, psoriasis, idiopathic thrombocytopenic purpura, lupus erythematosus, autoimmune hemolytic anemia, scleroderma, severe psoriasis, rheumatoid arthritis, and optic neuritis.
8. History of severe retinopathy or evidence of severe retinopathy judged by pre-entry ophthalmologic examination.
9. Known allergy/sensitivity to study drug or its formulation.
10. History of seizure disorders or current anticonvulsant use.
11. Any history of medical conditions associated with chronic liver disease (genetic hemochromatosis, alcoholic liver disease, toxin exposures, and autoimmune hepatitis) or documented cirrhosis due to any cause.
12. History of pulmonary disease associated with functional limitation.
13. Documented history of thyroid disease.
14. Active drug or alcohol use or dependence, which in the opinion of the investigator, would interfere with complying with the study requirements.
15. Known hypersensitivity to *Escherichia coli*-derived products such as filgrastim.
16. Any systemic illness that will make it unlikely that the subject will be able to return for the required study visits.
17. History of, or any condition that in the opinion of the investigator would interfere with the conduct of the study, or it would not be in the best interest of the subject to enroll in this study.

5 Schedule of Visits and Procedures

Participants will be seen in the NIAID/CCM Clinic at the NIH Clinical Center, NIH (PI: [name]) OR at the AIDS Clinical Trials Unit, Division of Infectious Diseases, University of Pittsburgh (PI: [name]; active enrollment at Pittsburgh was completed in 2014). We plan to enroll a total of 10 completed

participants for this study. Any dropouts and non-adherent participants will be replaced.

5.1 Screening (Days -58 to -28)

Screening will consist of HIV-1 RNA level and if < 50 copies/mL by standard assay and have detectable PBMC-associated HIV RNA ≥ 5 copies/million cells will continue with screening. If > 50 copies/mL, the subject will not undergo further screening assessments.

Screening for the protocol will be completed within 4 weeks prior to the study enrollment. During screening visit the protocol design will be reviewed, and informed consent will be obtained prior to any study-related screening procedures. The subject will then be given the consent document to read. Consent forms may be sent to the subject for review prior to the screening visit. The site investigator will review the study with the subject and answer any questions the subject may have about the study design, interferon, or study procedures. After the subject has read this information, there will be further opportunity for discussion with one of the investigators. Potential participants will sign consent prior to any study-related procedures. Once consented, eligibility will be assessed.

5.2 Pre-entry Visit 1 (Day-27 to Day -1)

When eligibility evaluation is complete, the subject will return for further assessments and the standard consent will be administered. The subject's medical history will be reviewed and a physical examination will be performed, including weight and vital signs. Concomitant medications will be documented. The assessments are summarized in Appendix 1, and include:

- Complete physical examination, including vital signs
- Beck Depression Inventory Scoring (BDS)
- Complete blood count with differential, platelet count
- Serum chemistries (sodium, potassium, chloride, carbon dioxide, creatinine, urea nitrogen, alkaline phosphatase)
- Creatinine clearance (Cockcroft-Gault method)
- Fasting blood glucose
- TSH, free T4
- Urine pregnancy test (women of childbearing age)
- Antinuclear antibody (ANA)
- Urinalysis
- Amylase
- ALT, bilirubin
- Hepatitis B surface antigen, hepatitis B surface antibody, hepatitis C antibody and hepatitis C viral RNA level (HCV PCR)
- CD4 count
- Ophthalmology examination (dilated funduscopy examination)
- Single copy assay for HIV-1 RNA
- HIV-1 RNA standard assay

- HIV-1 ELISA/Western Blot (if documentation not available)

5.3 Pre-Entry Visit 2: Leukapheresis Visits (Day -14 to Day -1, Day 28)

Once the subject has been found to meet the eligibility criteria, the subject will return for leukapheresis for the purposes of peripheral blood lymphocyte (PBL) storage for use in future virologic and immunologic studies. Leukapheresis, will be scheduled to occur at Pre-Entry 2 and during Visit 4 (Day 28).

5.4 Entry (Day 0)

Participants will have laboratory safety assessments performed and receive their first dose of PEG-IFN. Administration of pegylated interferon will be performed by trained personnel. Vital signs will be obtained, concomitant medications documented, and a targeted physical examination will be performed based upon any signs or symptoms that the subject has experienced since the last visit.

Assessments are detailed in Appendix 1 and include:

- Beck Depression Inventory score
- Complete blood count with differential, platelet count
- Serum chemistries (sodium, potassium, chloride, carbon dioxide, creatinine, urea nitrogen, alkaline phosphatase)
- Urine pregnancy test (women of childbearing age) prior to interferon administration
- ALT, Bilirubin
- Creatinine clearance (Cockcroft-Gault method)
- CD4 count
- Single copy assay for HIV-1 RNA
- HIV-1 RNA standard assay
- Interferon level (baseline)
- PBMCs for storage

5.5 Intensification Phase: Visit 1 (Day 7), Visit 2 (Day 14), Visit 3 (Day 21)

Participants will have laboratory safety assessments performed and receive their subsequent doses of PEG-IFN. Vital signs will be obtained and concomitant medications documented. Administration of interferon will be performed by study personnel. Dosing will be based on body weight obtained during initial evaluation. The last PEG-IFN administration will be on Day 21 (Visit 3). A targeted physical examination will be performed based upon any signs or symptoms that the subject has experienced since the last visit. Assessments are detailed in Appendix 1 and include:

- Beck Depression Inventory score
- Complete blood count with differential, platelet count (STAT, prior to interferon administration)
- Serum chemistries (sodium, potassium, chloride, carbon dioxide, creatinine, urea nitrogen, alkaline phosphatase)
- Creatinine clearance (Cockcroft-Gault method)

- Urine pregnancy test (women of childbearing age) prior to drug administration
- ALT, Bilirubin
- Single copy assay of HIV-1 RNA
- HIV-1 RNA standard assay
- Interferon level

5.6 Early Post-Intensification Phase: Visit 4 (Day 28)

Participants will have laboratory safety assessments performed. Vital signs will be obtained and concomitant medications documented. A targeted physical examination will be performed based upon any signs or symptoms that the subject has experienced since the last visit. Assessments are detailed in Appendix 1 and include:

- Beck Depression Inventory score
- Complete blood count with differential, platelet count
- Serum chemistries (sodium, potassium, chloride, carbon dioxide, creatinine, urea nitrogen, alkaline phosphatase)
- Creatinine clearance (Cockcroft-Gault method)
- ALT, Bilirubin
- CD4 count
- Single copy assay of HIV-1 RNA
- HIV-1 RNA standard assay
- Interferon level
- PBMCs for storage
- Leukapheresis

5.7 Late Post-Intensification Phase: (Visits 5 to 9)

Participants will return for visits at Days 35, 42, 49, and 56 during the pegylated interferon post-intensification phase. The Assessments are detailed in Appendix 1 and include:

- Beck Depression Inventory score
- Complete blood count with differential, platelet count
- Serum chemistries (sodium, potassium, chloride, carbon dioxide, creatinine, urea nitrogen, alkaline phosphatase)
- Creatinine clearance (Cockcroft-Gault method)
- ALT, bilirubin
- Single copy assay for HIV-1 RNA
- HIV-1 RNA standard assay
- CD4 count (Visits 8 and 9)

5.8 Long-term Follow-up: Week 16 (Visit 10)

The following determinations will be assessed at the Week 16 visit:

- Beck Depression Inventory score
- Complete blood count with differential, platelet count

- Serum chemistries (sodium, potassium, chloride, carbon dioxide, creatinine, urea nitrogen, alkaline phosphatase)
- Creatinine clearance (Cockcroft-Gault method)
- ALT, bilirubin
- Single copy assay for HIV-1 RNA and assays for cell associated HIV
- HIV-1 RNA standard assay

5.9 Weeks 24 and 36 (Visits 11 and 12)

The following determinations will be assessed at the Week 24 and Week 36 visits:

- HIV-1 RNA standard assay
- Single copy assay for HIV-1 RNA and assays for cell associated HIV

5.10 Week 48 (Final Visit, Study Discontinuation Visit)

The following determinations will be assessed at the Week 48 or Study Discontinuation visit:

- Beck Depression Inventory score
- Complete blood count with differential, platelet count
- Serum chemistries (sodium, potassium, chloride, carbon dioxide, creatinine, urea nitrogen, alkaline phosphatase)
- Creatinine clearance (Cockcroft-Gault method)
- ALT, bilirubin
- Single copy assay for HIV-1 RNA and assays for cell associated HIV
- HIV-1 RNA standard assay
- CD4 count
- PBMC

5.11 Window Periods for Study Visits

The following variable scheduling is permitted for study visits:

Days -58 to 14: ± 1 day

Days 21 to 49: ± 2 days

Days 56 to 84: ± 5 days

Weeks 16 to 48: ± 14 days

6 Concomitant Medications

All concomitant medications will be documented at each study visit.

Concomitant administration of immunomodulatory treatments (including steroids, radiation, IL-2, and anti-neoplastic agents) is not allowed during the course of this trial. Other investigational drugs are excluded. No vaccinations are allowed during the study period from 30 days prior to the time of signing consent to the end of the four week interferon therapy period.

7 Study Drug Administration

7.1 Drugs and Dosing

All participants will receive pegylated interferon alpha 2b at the dose of 1.5 µg/kg subcutaneously every week for 4 doses. Dosing will be determined at Entry, and Visits 1, 2, and 3 based on subject's body weight obtained at the time of enrollment. Administration of study medication will be performed by study personnel. Antiretroviral therapy will be continued throughout the study.

7.2 Monitoring Parameters

The Schedule of Events is found in Appendix 1. Participants will be closely monitored for clinical and laboratory evidence of adverse events associated with the study drug or medical complications.

7.3 Dose Modifications/Toxicities

A complete blood count with differential (done STAT) will be reviewed before PEG-INF administration at visits 0, 1, 2, and 3. Participants experiencing an adverse event Grade ≤2 may continue at their current dose. No interferon dose modifications will be made in the study but additional visits or monitoring will be permitted to evaluate participants. Toxicity will be evaluated using the Division of AIDS Table for Grading Adults Adverse Events: (<http://rcc.tech-res.com/safetyandpharmacovigilance/>).

8 Management of Toxicities to Study Drug

